### **Study Population**

In FY 2012-13, 2,297 Family PACT clinician providers served over 1.5 million female Family PACT clients. A detailed description of the Family PACT services can be found in the Family PACT Program report for FY 2012-13. Women eligible for these services are uninsured women, under 200% of the federal poverty level, at risk of pregnancy. Sixty-three percent of Family PACT female clients are less than 30 years of age and about 50% are within our target age group: 21-29 years. Sixty-three percent define themselves as Latina and 38% report that Spanish is their primary language. Twenty percent identified as white and 6% as black. Eighty percent were below the Federal Poverty Guidelines. Retention at clinics is quite high. Defining retention as having used Family PACT at least once in four years prior to their visit in FY 2012-13, 74% were retained in care. The program serves a disproportionately high number of Latinas. Fifty-three percent of the entire Family PACT population is Latina, whereas 19% of the entire California population is Latina.

Our goal is to identify 14 provider sites that each serve at least 200 female clients aged 21-29 years that are willing to participate in study and be randomly assigned to one of the two research arms. We will also identify sites with similar inclusion criteria who but are not participating and of these, 7 sites will be randomly selected for comparison so that this comparison arm would result in a similar number of women aged 21-29 years. We will use variables from the following Family PACT administrative databases to determine the sampling universe: Provider enrollment, client enrollment, and claims databases. We excluded Family PACT providers who are Planned Parenthood (PP) affiliates from our sampling universe because they have a unique monitoring and tracking system of cervical cytology testing that assures adherence to guidelines hence, they would not be representative of other primary care settings. We will also exclude those that already have on average long intervals (>30 months) since they likely already adhere to guidelines. To maintain efficiency, we will focus on Southern California sites that serve the greatest number of women. These include Los Angeles, Orange, San Diego, Riverside, Santa Barbara, San Bernardino, Imperial, Kern, Ventura, and Fresno counties. Within these counties, there are 1,114 private sector clinics, 456 public sector clinics serving a total of 1,280,846 clients. The average age of these women is 27.4. Sixty-nine percent identify as Latina, 15% as white, 6% as black, and 7% as Asian/Pacific Islander. Forty-six percent state that Spanish is

there primary language. Sites that send their cytology to Quest laboratories will also be identified to allow for consistent cytology collection medium and processing.

## **Selection of Participants**

### *Inclusion Criteria*

#### Intervention arms:

We will identify Family PACT providers who meet the following inclusion criteria:

- Is located in one of the ten Southern California study counties
- Clinical care visits occurred to at least 200 women aged 21-29 years in FY 11/12
- Has a calculated average cytology interval of < 30 months (based on last 3 years)
- Cytology is sent to Quest laboratories

For comparison, we will select from the following:

- Is located in one of the ten Southern California study counties
- Clinical care visit occurred to at least 200 women aged 21-29 years in FY 11/12
- Has a calculated average cytology interval of < 30 months (based on last 3 years)
- Cytology is sent to Quest laboratories

## **STUDY METHODOLOGY**

### **Study Intervention**

#### *Choice of Comparators*

We will compare 2 different interventions arms that are designed to prevent overscreening and over treatment by increasing adherence to the new US cervical cancer screening guidelines and the ASCCP guidelines for the management of abnormal cervical cancer screening tests and cancer precursors. Specifically, the interventions will focus on lengthening cervical cancer screening intervals to every 3 years, decreasing colposcopy procedures for minimally abnormal cytology results and decreasing treatment of cervical precancerous lesions with a high rate of regression (i.e., cervical intraepithelial neoplasia grades 2 and 2/3).

The two arms will be:

- 1) Mobile application (APP)-based intervention for providers,
- 2) Mobile application (APP)-based intervention for providers PLUS patient-centered approach intervention (PCA).

The two arms will be compared to a comparison group (no intervention).

The APP-based intervention (APP) is for clinicians' mobile phones and will maneuver them through current guidelines (cervical cancer screening and management of abnormal cytology and histology) based on patient age and condition. This is the current ASCCP tool, which will be updated to include screening guidelines and risk assessment so the provider can better understand the risk associated with follow-up versus premature triage to colposcopy.

The patient-centered approach intervention (PCA) is oriented towards educating women about HPV and cervical cancer screening. The intervention will be provided to patients' when they check-in for a clinic appointment, and will interactively provide information designed to help them understand current guidelines for the frequency of cervical cancer screening and appropriate management for abnormal cytology and treatment options. It will allow them to assess the risks and benefits of screening intervals and of treatment choices.

Comparison sites will have no intervention.

This approach will allow us to examine what the additional benefit of educating women and providers would be over educating providers only. Our design also underscores downloading of mobile applications are passive and does not equate with knowledge of or use of the mobile application. Within the intervention arms, providers will be systematically educated on all the functions and capabilities of the mobile application and to ensure that the application is used consistently.

The comparison group is likely to include providers who have already downloaded and use the application. But this group would not have been systematically educated as to how to use the application, hence allowing us to examine the role of education around the integration of the mobile application into counseling.

### *Development of the PCA Intervention*

Four focus groups will be held both English and Spanish speaking, separately. With the assistance of NCCC and LCC, our patient stakeholders women aged 21-29 years of age will be identified for each focus group (See **Appendices A & B** for Focus Group Scripts). The focus groups will review the guidelines and their rationale and ask women what messages would be most appropriate and acceptable to the target population. Women with cancer, CIN and no abnormal cervical cytology will be targeted for inclusion whenever possible. Women who have never been screened for cervical cancer also will also be sought to participate. Issues that will be addressed include fears, concerns, and areas of uncertainty she may have around screening, and potential messages that could be used to address these issues. Thematic areas will focus on: cervical cancer screening intervals in young women under 30 years; natural history of HPV, follow-up of ASCUS and LSIL cytology by cytology only in women aged 21-24 years vs. immediate referral to colposcopy, follow-up of biopsy proven LSIL by cytology without treatment, follow-up of biopsy proven HSIL by colposcopy and cytology vs. immediate treatment, treatment options (cryotherapy vs. excisional therapy).

Transcriptions of the oral discussions of the focus groups will be taken and distributed to the group. Based on the transcriptions, we will develop a paper tool.

#### ***Themes within in the intervention include:***

- Defining what is a Pap smear
- Defining what is a cervix
- The relationship between HPV infections and Pap smear
- The natural history of HPV (clearance versus persistence) and its relationship to cervical cancer
- Perceived Importance of Pap smears
- The risk benefit ratio of overscreening
- The risk benefit ratio of overtreatment
- Understanding cervical cancer screening interval recommendation
- Understanding HPV testing recommendations
- Understanding how the new guidelines were established
- Understanding the new guidelines for abnormal cytology

Once the research and stakeholder team review the paper tool and agree to its flow and content, 5-10 women, with a history of normal cytology, no history of screening and abnormal cytology will be solicited through the stakeholders (NCC and LCC) as well as flyers (See **Appendices C & D**) at clinics and bus stops to participate in a cognitive interview (See **Appendices E & F**). Women will be walked through the paper tool and address clarity, cultural sensitivity, and appropriateness of messaging. All interviews will be recorded and transcribed. Both English and Spanish speaking women will be identified. Changes will be incorporated after each feedback (if time permits) and incorporated before the next interview. (See **Appendices G to J** for Final Paper tools)

### *Technology Design*

**Media:** A URL based app will be developed and tested. After each testing, notes will be taken by the SC and then reviewed by the team for clarity, flow, interest, and ease of use. NCCC and LCC will be asked to review and give feedback. Ten women will then be asked individually to review the URL and give feedback in a one to one setting. The URL website allows us to easily make changes over time as input is given.

**Userface design:** The media will be a combination of pictures, words, short videos and interactive buttons in order to engage and hold the attention of the woman.

The application will be developed using a responsive design approach—a website optimized for viewing on a tablet or phone allowing the app to be used on both iOS and Android devices as well as easily distributed later. The responsive design approach will allow the incorporation of videos and animation using HTML 5. During the study, the app will be distributed to clinics through a URL: <http://medschool2.ucsf.edu/preview/dots/site/>.

The application will be both unit and functionally tested to work in the targeted tablet devices and browsers identified by the study team. In addition, the study team will work with the identified clinics to ensure wireless coverage.

The tablet will not be set up to collect any data on individuals.

### *Final Product Development*

The final URL will be reviewed and edited by the team (research and stakeholders NCC and LCC) until the group agrees on all content, flow and messaging feedback. The application will allow women to choose English or Spanish language. Then they woman will be able to choose whether she is there because she had an abnormal Pap smear or not.

#### Content for cervical cancer screening (no current history of abnormal cytology)

- Introduction to Pap smears
- Description of normal anatomy including cervix, uterus, fallopian tubes
- How a Pap smear is obtained
- What Pap smears look for (abnormal cells)
- What is the connection between HPV (what is HPV) and Pap smear
- How common is HPV
- Risk of cervical cancer
- Importance of Pap smear
- When women should first get screened
- How often women should get screened
- Risks and Benefits to increased intervals
- Screening for women with HIV and other immunosuppressive disorder
- How women can protect themselves; through HPV vaccination, condom use, stop cigarette smoking and getting tested regularly for STIs
- Questions women might want to use to ask their provider

## Self-assessment Quiz (See **Appendices K & L**)

### Content for history of current abnormal cytology

Introduction to Pap smears

Description of normal anatomy including cervix, uterus, fallopian tubes

How a Pap smear is obtained

What Pap smears look for (abnormal cells)

What is the connection between HPV (what is HPV) and Pap smear

How common is HPV

Risk of cervical cancer

What is an abnormal Pap test

Relationship between abnormal Pap test and cervical cancer

What happens next if I have an abnormal Pap test

Description of colposcopy

Description of a biopsy

What happens after colposcopy

What type of procedures are available for treatment

Questions around partner treatment and transmission

How women can protect themselves; through HPV vaccination, condom use, stop cigarette smoking and getting tested regularly for STIs

Questions women might want to use to ask their provider

Self-assessment Quiz (See **Appendices K & L**)

### *Final Pilot Testing*

We will ask an additional 5-10 women recruited by NCCC, LCC and local women to participate in individual interviews to pilot test the program in a simulated clinical environment. Women who have had LSIL, HSIL, colposcopy with biopsy, and never screened will be solicited. The only introduction that will be given will be that similar to what will be given at the clinic sites. They will be asked to complete this education/self-assessment tool about cervical cancer screening and treatment options in accordance with their clinical history. These visits will be conducted by members of the research team and feedback sessions will be audio recorded. Immediately after using the intervention, the woman will complete a semi-structured interview that reviews her general reactions to the tool and her feedback and suggestions for specific components. Attention will be paid to the appropriateness of the information provided, both with respect to content and format, and the degree to which the tool addressed the common concerns women may have in each area. We will also explore whether the layout and navigation of the tool are accessible and clear. Specifically, we will ask whether she feels the tool helped in hearing the information and making decisions for cervical cancer screening intervals as well as treatment or follow-up. The study team will also debrief on the perceived influence of the tool on the potential clinical interaction with their provider. This information will be brought back again to the team and any modifications will be made to the intervention. Following completion of 4-5 interviews, the study team will meet and discuss changes to the tool based on the feedback and implement these changes. This process will be then be repeated in an iterative manner with 5 additional women if needed.

Final product will be an interactive, computerized, educational tool for cervical cancer screening and management of abnormal cytology and histology which will be informed by patients' preferences and experiences of cervical cancer screening, colposcopy, biopsy and treatment as well as by the medical expertise of guideline experts. This tool will be designed to facilitate the counseling interaction by providing the patient with information about her options and assisting her in identifying her preferences and areas of uncertainty and is intended to assist the patient in determining important areas for discussion during the visit.

The final product will be approved by NCC, ASCCP, LCC and all investigators. ACOG (Committee on Adolescent and young adult) will be asked to review for their input.

### *Development of the Mobile Application Based Intervention for Providers*

Currently, the ASCCP has designed a mobile application for the management of abnormal cytology and histology guidelines based on the 2006 management of abnormal cytology and histology guidelines and the recently released updated guidelines: 2012 Updated Consensus Guidelines for the management of abnormal cervical cancer screening tests and cancer Precursors. The mobile app can be purchased for both iPhones through the Apple store and Androids through Google Play. Both the iPhone and Android version of the App will be updated with PCORI support to help providers assess risk as well as provide guidelines for screening. Risk assessments will help providers understand the need to refer to colposcopy versus to watch observantly and to treat versus watch observantly. This effort will also involve National Cancer Institute. For example, young women with LSIL on cytology is a low risk for CIN 2/3, hence the management recommended is repeat cytology in one year not colposcopy. The risk associated with the development of CIN 2/3 is given under these circumstances. The American Cancer Society screening guidelines will also be added. For this application, there is no data exchange nor data collection – it will simply be a decision tool for the doctor.

## **Study Implementation Procedures**

### *Study Enrollment Procedures*

#### Contacting sites:

A letter will be sent to all clinic administrators of eligible sites explaining the study. A follow-up phone call will occur one week later. We will explain the study over the phone and those interested and agree to participate will be identified as clinics eligible to randomize to an intervention arm. If more than 14 sites agree to participate, we will let the sites know that they may not be asked to participate. If more than 14 sites agree, the 14 sites will be chosen based on identifying a balance of private and public clinics so that the average number of women aged 21-29 years is 500, and a relative geographic distribution among the 10 counties and that both English and Spanish languages are well represented according to the county's proportion of Hispanics.

Of those eligible for the comparison sites, we will identify sites using the eligibility criteria, and randomly identify 7 sites but with matching for private and public clinics and relative size of

practice which may range from 200 to over 1000 clients. There will be no contact with these sites since the outcomes data will be monitored from the Family PACT claims database.

Randomization:

Block randomization of clinics to one of the two arms will be performed by the biostatistical group at UCLA.

Site set up:

[name] and the PC will visit all 14 identified clinics sites to meet with staff, identify a key contact person for the site, discuss flow issues, and discuss the protocol.

***For clinics randomized to APP-based intervention alone (arm 1):***

We will ask each of the providers to download the ASCCP application prior to the in-service or at the beginning of the in-service. We will meet with each of providers in the practice in person for a 30-minute session to introduce them to and provide basic guidance to the ASCCP mobile application. This will include showing them the screening guidelines on the application, and using several scenarios as examples to practice its use. These will all focus on women under 30 years of age. If any new providers are hired during the period, the PC will come out to provide them with orientation to the web based application. It is expected that some of the providers will already have the APP. We will ask them to participate in the in-service as well.

***For clinics randomized to APP with PCA-based intervention (arm 2):***

In addition to the training described above for the providers, we will work with clinic staff randomized to this arm to optimize implementation of the patient-directed application. First, staff will be introduced to the goals of the application, and will be taken through it in an interactive manner, allowing for questions and answers. The PC will train staff in using the website, how to connect to and open the URL, and begin the application. The intervention is expected to be easy to use but in case the clients have questions, the staff will be trained.

For implementation, we will work interactively with the clinic staff to make sure the tablet is provided as part of normal clinic flow. This may involve the front desk or nursing visit during vital signs depending on the clinic. The SC will work closely with the site to make sure all age appropriate (21-29 years) are given a tablet at the time of their visit. Instruction will be given how to interact with the patients regarding assessing their interest and giving them the website information for their own devices or use of the tablet we provide the clinics. The tablet will be either held with the staff (encased in a large case in order to deter theft) or will be locked to a specific site in the waiting room, depending on the configuration of the clinic. For those sites with no Wi-Fi connectivity, we will purchase a monthly Wi-Fi subscription for the tablet.

Adherence:

Although we will not have site-specific data, we will be able to see how many times the PCA has been viewed.

### Comparison Arm:

No site set up will be performed with comparison groups.

### *Quality Assurance*

The PC will identify a point of contact for each intervention site with whom to maintain monthly contact via email/telephone, depending on the type of interaction the site staff requests to ensure that the tablet is functional and remind them to use it in clinic flow. We will ask approximately how many times a week the tablet is being used, how many women refused (in the 21-29 year old), how many women were not offered the tablet. We initially will make weekly calls/emails. After the first month, we will make monthly contact.

The PC will visit all participating intervention arm clinics 2-3 times a year. At that time the PC will ensure that the interventions are in place -- tablets are being functional and are being offered to all age-appropriate women attending the clinic, and all provider phones have a functional mobile application. In addition, to collecting satisfaction surveys, the PC will also collect data on any potential factors that may bias or contaminate an arm (i.e., webinars attended by staff on cervical cancer screening, mobile apps present on the other intervention arms, among others.) using the Quality Assurance Survey (See **Appendix M**). This will be collected at the end of the first and second years. Sites will be reimbursed \$1,000 each a year for their participation in the Quality Assurance Project.

### *Satisfaction Survey*

The PC will attend all the clinics 2-3 times a year. At this time, women attending the clinic and complete the tablet intervention will be asked, after consenting, to complete a satisfaction survey (See **Appendix N**) at the end of the visit that will ask the patients, age, cytology diagnosis, and whether the tool was useful, easy to use and did they feel it gave them adequate information regarding cervical cancer screening guidelines and treatment options. Forty women from each of the sites (200 for each arm) will be solicited years 2 and 3.

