The primary outcome measure will compare the observed within-clinic changes in cervical cytology testing rates between intervention and comparison groups using a t-test accounting for clinic-level clustering. We will use the same approach to test differences between each of the APP and APP + PCA and the comparison groups. Tests will be adjusted for multiple comparisons. Secondary endpoints include examining the interval between tests for women who received two cervical cytology tests from the same provider and the decrease in the number (and percent) of women receiving colposcopy procedures and LEEP or cryotherapy procedures. These will be analyzed using a similar approach as adopted for the primary endpoint. Patient satisfaction surveys will be administered to all women evaluated and compared between interventions and the controls. Because most available data is on the clinic level, we will have limited opportunities to analyze patient-level data. However we will be able to conduct supplementary analyses to investigate the possible impacts of between-arm imbalances in clinic level characteristics such as racial/ethnic composition, age distribution, descriptors of lab procedures, additional app or educational materials that are not part of the assigned intervention, and cervical cancer screening educational activities. Prior to starting the intervention and during the study, administrators and physicians at each clinic site will be asked about possible confounding variables at their clinic.

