### Potential Risks

Focus groups, interviews and mock pilot testing: Potential risks are low in all three formats. Inadvertent disclosure of patient's condition such as having cervical cancer may cause embarrassment or psychological distress in the focus groups. For the focus groups and interviews, discussion about procedures that previously caused distress may invoke stress. Since these women are volunteers and it will be explained to them ahead of time, it is likely that these risks are extremely low. Women who will try the mock intervention are not likely to have any risks unless as above, it induces stress given a past situation.

*Randomized Intervention Trial:* Risks for participation are low. It is possible that completing the tablet intervention will induce anxiety, however, input from the community stakeholders and patients during the development of the app should keep this to an extremely rare event, if ever. Women do not have to complete the tablet intervention and they can stop it any time. The tablet will be voluntary at the clinic sites. No PHI will be collected from the tablets on the women for this study nor shared with investigators. Data from the tablets is not stored anywhere including the risk assessment. It will be deleted immediately after clients complete the survey.

*Patient Satisfaction Survey:* Risks for participation are low to none. Patients will be asked about age and condition but no personal identifiers will be collected. Information about ease of tablet use will be asked as well as whether the tablet was informative and helpful.

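### The plan gives two different populations for the satisfaction survey, and under the operational one, women who open the patient tool and stop part-way are neither asked nor counted

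*Combined protocol and SAP*

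**What the plan says.** The Satisfaction Survey section (Study Implementation Procedures) sets the entry condition: "women attending the clinic and complete the tablet intervention will be asked, after consenting, to complete a satisfaction survey". The survey covers age, cytology diagnosis and "whether the tool was useful, easy to use and did they feel it gave them adequate information". Its target is a count: "Forty women from each of the sites (200 for each arm) will be solicited years 2 and 3".

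Data Analyses (Analytic Methods) describes the population differently: "Patient satisfaction surveys will be administered to all women evaluated and compared between interventions and the controls". It does not define who counts as evaluated and gives no procedure for reaching them.

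Four other places bear on who ends up in the survey:

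- Potential Risks makes the tool voluntary: "Women do not have to complete the tablet intervention and they can stop it any time".
- The arm 2 procedures offer two routes to the same web-based tool, "giving them the website information for their own devices or use of the tablet we provide the clinics", and state under Adherence that only an overall number of views, not split by site, will be available.
- Quality Assurance asks site contacts for approximate weekly use, and "how many women refused (in the 21-29 year old), how many women were not offered the tablet".
- Technology Design says that the tablet collects nothing on individuals.

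**The concern.** A survey that requires completion removes by rule the women who began the tool and gave up. They are the users best placed to say that it was hard to follow or unhelpful. They may also include women affected by the one risk that the plan names for the tool: "It is possible that completing the tablet intervention will induce anxiety".

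The survey has a use during the trial. Progress Review lists it among the inputs to meetings that may change the protocol or the interventions. A rating taken from completers and read as the view of all users could make the tool look easier or more welcome than it is. The Missing Data section promises to examine whether missing information, including survey information, is related to patient, clinic or arm factors. That cannot be done for women who are never approached and for whom nothing is recorded.

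**Working it through.** **1. The plan's own figure.** The Satisfaction Survey section gives 40 women per site and 200 per arm. The Study Design Overview gives 7 sites per arm. 40 × 7 = 280, not 200; 200 / 40 = 5 sites. The figure does not reproduce and should be corrected in the same edit, but it has no bearing on who is selected. What matters here is that the target is a fixed count. Forty completers can be found at a site whatever share of women finish, so high drop-off would leave no trace in the survey.

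**2. Where each group of women is recorded, if the Satisfaction Survey section governs.**

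- Not offered the tool: approximate site report (Quality Assurance). Not surveyed.
- Offered, declined: approximate site report (Quality Assurance). Not surveyed.
- Opened, stopped part-way: permitted (Potential Risks). Not surveyed. Quality Assurance does not ask for them, the tablet holds no individual data, and a view count does not separate a started session from a finished one.
- Opened, completed: surveyed, if present on a visit day and consenting.
- Used own device: status not stated.

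The third group is the one with no data at all. Potential Risks uses the same verb, completing, in contrast to stopping, which supports reading the survey condition as finishing the tool rather than merely using it.

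**3. Size of the shift.** Let c be the share of women opening the tool who complete it, s_c the share of completers who are satisfied, and s_n the share of non-completers who are satisfied. Satisfaction among all openers is c × s_c + (1 − c) × s_n. A completer-only survey reports s_c, so

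gap = s_c − [c × s_c + (1 − c) × s_n] = (1 − c) × (s_c − s_n).

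The documents give none of the three inputs. All values below are assumptions.

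- c = 1, any s_n: gap = 0.
- s_n = s_c, any c: gap = 0.
- c = 0.90, s_c = 0.90, s_n = 0.80: 0.10 × 0.10 = 1 point.
- c = 0.75, s_c = 0.80, s_n = 0.60: 0.25 × 0.20 = 5 points.
- c = 0.75, s_c = 0.90, s_n = 0.60: 0.25 × 0.30 = 7.5 points.
- c = 0.50, s_c = 0.90, s_n = 0.30: 0.50 × 0.60 = 30 points.

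**4. Against sampling error.** With the stated 200 women and 90% satisfied, ignoring clustering by site, the 95% half-width is 1.96 × √(0.9 × 0.1 / 200) = 4.2 points. With 280 women it is 3.5 points. A 1-point shift would be lost in this. A 7.5-point shift would exceed it, and surveying more completers would not reduce it.

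**The case against.** Much of the other side's case stands.

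- **The plan does not say only completers throughout.** Data Analyses has a wider population. That makes this first a contradiction to be resolved. It does not close the gap, because the Satisfaction Survey section is the one that tells site staff whom to approach.
- **A reader might infer that women using their own phones are excluded.** The documents do not say so. The tool is a single website offered on either device, and Potential Risks uses the tablet as a general name for it. Their status is unclear, no more.
- **A reader might infer that acceptance of the tool is overstated and that decliners go unseen.** The survey measures satisfaction, not uptake, and refusals and non-offers are asked for separately, if only as rough site reports. A woman who never opened the tool cannot rate its ease of use, so limiting those items to users is a normal choice. The gap that remains concerns women who opened the tool and stopped.
- **The direction is an inference.** Some women may stop only because they are called in to be seen, and may be as satisfied as the rest.
- **Worry may already be covered.** The section only summarises the questions, and the form itself (Appendix N) is not in the text. Whether an item on worry is missing cannot be checked.
- **Nothing in the trial's main conclusions rests on the survey.** This is correct and sets the weight of the point.

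**Conclusion.** The two sections define different survey populations and must be reconciled. If the Satisfaction Survey section governs, the results describe completers, and women who open the tool and stop are counted nowhere. Satisfaction is then likely, but not certainly, higher than among all women who opened the tool. The likely direction rests on the assumption that women who stop are, on average, less satisfied than those who finish.

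The size is unknown. The 0 to 30 points above show how the gap depends on two unrecorded quantities: the completion share and the difference in satisfaction. They are not an estimate, and a reader should not conclude that a particular overstatement has been shown.

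The weight is minor. The primary endpoint and the listed secondary endpoints come from Family PACT claims and are unaffected. The survey is one of several inputs to Progress Review.

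**What to change.** Reword the Satisfaction Survey section, and Data Analyses to match, as follows.

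1. Survey all women aged 21-29 in the APP plus PCA arm who opened the tool, on the clinic tablet or their own device, on survey days. State that own-device users are included.
2. On those days, log how many women were offered the tool, declined, started and completed it.
3. Report satisfaction among all who opened the tool and, separately, among completers, beside those shares.
4. Correct the per-site and per-arm targets so that they agree. Remove or rework the comparison with controls, since the Comparison Arm and Study Enrollment Procedures text allows no contact with comparison sites.

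The cost is small, because the coordinator already visits 2-3 times a year. If the target stays at 40 per site and counts openers, no extra forms are needed. If 40 completers per site are wanted and, say, 75% complete, then 40 / 0.75 = 53.3, so 54 openers: 14 extra forms and 14 × $10 = $140 in gift cards per site. At 50% completion it is 80 openers, 40 extra forms and $400 per site. The survey consent wording may need revision, and the headline satisfaction figure will probably be lower. The primary analysis does not change.
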